In addition to the primary outcome this will allow us to extract data for the period 6 months prior to randomisation as a covariate and other outcomes including all offences and specific substance use offences as secondary outcomes. Frequency of substance use will be assessed at 6-months using the Time Line Follow Back Method (TLFB; (Sobell and Sobell, 1995, Levy et al., 2004)), a valid and reliable tool for assessing the frequency and quantity of multiple substances (Martin-Willett R et al., 2020) over time periods ranging from 1 to 365 days and

validated specifically for adolescents (Levy et al., 2004) and used in studies of adolescents in criminal justice settings (Coulton S et al., 2023, Dakof et al., 2015). To minimise burden, we will use the 28-day version which takes about 10 minutes to complete and demonstrates an excellent level of agreement with longer versions. This tool allows us to derive the percent days abstinent from substance use and allows derivation of several other outcomes over the period (e.g., quantity and type of substances consumed). As there is evidence of assessment reactivity associated with TLFB in brief intervention studies we will only measure TLFB at 6-months and employ a single frequency of substance use question at baseline for inclusion in the analytical model as a covariate.

Mental health and wellbeing will be assessed using the Warwick-Edinburgh Mental Well-being scale (WEMWBS; (Clarke et al., 2011)). WEMWBS is a 14-item, self-completed scale addressing different aspects of eudemonic and hedonic mental health wellbeing. Health-related quality of life will be derived from a short five level, five domain instrument used extensively in this population (CHU-9D;(Furber and Segal, 2015)).

Emotional regulation and behaviour will be assessed using the self-completed Strength and Difficulties questionnaire (SDQ; (Goodman, 1997)). This assesses behaviour across several domains, conduct, hyperactivity, emotional regulation, peer relationships and prosocial. Self-reported offending will be assessed using the Self-Report Delinquency Scale (SRDS; (Smith and McVie, 2003)) over the previous six months. All these instruments will be assessed at baseline and 6-months.

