Three exploratory analyses will be undertaken.

The mechanism of change will be explored using a mediation model approach and incorporating motivation (RR), self-efficacy (SCQ-8), and expectancy (SUE) at 6-months, adjusted for baseline covariates. Allocated group will be included as an interaction term.

Stepwise regression analysis will be performed to model the relationship between prerandomisation factors; age, gender, ethnicity, IMD, BFRS, ACEQ, GAD-7, PHQ-9 and observed outcomes at 6 months, separately for the primary outcome and PDA substance use. Interaction terms with allocation arm will be included in the analysis, and a significance level of 0.1 will be used to determine which factors are to be included in the regression model. Prerandomisation factors will include gender, age, ethnicity, IMD decile, adverse childhood experiences, anxiety and depression and family cohesion. This analysis will be augmented by an additional analysis including participants in the intervention arm only using the same prerandomisation factors but also including process measures of adherence, intervention fidelity, therapeutic alliance, interventionist, and interventionist perceptions.

Interim analyses and stopping rules

No interim analyses are planned.

Longitudinal follow-up analyses

Proposed outcomes at each stage of the evaluation

Assessments are conducted at baseline and then at six months post-randomisation, the latter being the primary endpoint. Table 2, indicates outcomes assessed at each end-point.

Outcome	No. of Questions	Baseline	Month 6
Frequency of substance use (Single TLFB item)	1	~	
Time Line Follow-Back 28-day version ¹	0		\checkmark
Wellbeing (WEBWMS)	14	~	~
Quality of Life (EQ5D-5L)	5	\checkmark	\checkmark
Strength & Difficulties (SDQ ²)	25	~	~
Self-report Delinquency (SRDS ^{1,2})		~	\checkmark
Motivation state to change (RR)	1	~	~
Substance Use Expectancy (SUE)	4	~	\checkmark
Self-efficacy (SCQ-8)	8	~	\checkmark
Generalised Anxiety Scale (GAD-7)	7	\checkmark	
Depression - Personal Health Questionnaire (PHQ-A)	8	~	
Adverse Childhood Experiences (ACEQ)	10	\checkmark	
Brief Family Relationships Questionnaire (BFRS)	16	\checkmark	

 1 TLFB28 and SRDS are researcher led questionnaires rather than client self-completed 2 SRDS and SDQ are YEF Core outcomes

Imbalance at baseline

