Rather than just assume the randomisation has worked, we will assess observed balance by comparing the means and distributions of the groups created by randomisation. If they are systematically different across those variables we observe – e.g. always larger / smaller in one group - then that would suggest the randomisation has not been successfully implemented. Baseline equivalence following randomization will be assessed by first looking at allocation by the two stratifying variables, site and age group, and then extending the comparison by key outcomes, mean offences at baseline and mean days using substances at baseline.

Baseline characteristics will be summarised by randomised group. Summary measures for the baseline characteristics of each group will be presented as mean and standard deviation for continuous (approximate) normally distributed variables, medians and interquartile ranges for non-normally distributed variables, and frequencies and percentages for categorical variables. Following CONSORT when comparing treatment and control groups we will not use statistical tests.

If there is a large imbalance between groups on a specific variable, then that variable will be included in the analysis model. If there are systematic differences across multiple variables that are indicative of failed randomisation then it would be necessary to explore alternative analysis methods to estimate treatment effects, such as instrumental variable models, using treatment allocation as the IV.

Missing data

The proportion of missing data and patterns of missingness will be examined for the primary outcome. Levels of missing data will be reported along with any systematic occurrences of missing data observed in the dataset.

We will explore the mechanism of missing data to establish whether the data can be considered missing completely at random or missing at random. For each treatment arm, participants will be grouped based on their dropout time, and means at baseline and each time will be examined to assess whether there are systematic differences between those who dropped out at specific time points and those who remained in the study.

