To avoid loss of efficiency, missing outcome values will be imputed using multiple imputation for chained equations. This approach will only be undertaken if the proportion of missing data is greater than 5% and less than 40%. Where there is less than 5% missing data, the proportion of missing data is considered negligible and missing observations will be excluded. Multiple imputation methods perform less well when the amount of missing data is substantial, if more than 40% of the primary outcome data are missing the assumptions underlying the primary analysis are less plausible. Data will be analysed without imputation and the interpretative limitations of the trial data will be discussed in the results section.

An imputation model, containing all potential prognostic baseline covariates will be used. The number of imputations will be dependent on the amount of missing data, as a minimum the number of imputations will be derived to ensure at least 96% statistical efficiency (RE) according to the formula below (Eq. 2), where λ is the fraction of missing values and M is the number of repetitions.

Eq. 2

$$RE = \left(1 + \frac{\lambda}{M}\right)^{-1}$$

The statistical model and assumptions made in the analysis of the primary outcome will also be implemented in the multiple imputation procedures. If it is suspected data is missing not at random or the pattern of missing data is associated with trial allocation, sensitivity analysis will be performed using a pattern mixture approach with mixed modelling and multiple imputation to compare the sensitivity of conclusions to varying assumptions about the missing value mechanism. All available data from baseline to the time of dropout will be included in the sensitivity analysis using a repeated measures mixed effects model.

Compliance

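### The SAP's missing-not-at-random analysis states no departure from missing at random, and the only model it describes repeats the main answer when there is a single follow-up

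*SAP*

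**What the plan says.** The SAP (Longitudinal follow-up analyses) fixes the visits: "Assessments are conducted at baseline and then at six months post-randomisation, the latter being the primary endpoint".

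The SAP (Missing data) has three relevant parts:

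- To explore the mechanism, "participants will be grouped based on their dropout time, and means at baseline and each time will be examined".
- The MNAR analysis has two alternative triggers: "If it is suspected data is missing not at random or the pattern of missing data is associated with trial allocation".
- If either is met, "sensitivity analysis will be performed using a pattern mixture approach with mixed modelling and multiple imputation to compare the sensitivity of conclusions to varying assumptions". The sentence after that names the model, a mixed-effects model for repeated measures, and the data it uses: "All available data from baseline to the time of dropout will be included".

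The protocol (Analysis) also plans pattern-mixture and multiple-imputation sensitivity analyses contrasting MAR with MNAR, but attaches no condition.

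On TLFB, the protocol (Secondary outcomes) says "we will only measure TLFB at 6-months and employ a single frequency of substance use question at baseline", and the assessment schedules in both documents agree. The protocol's trial design table and the SAP's Design overview nevertheless list TLFB28 among the baseline measures.

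**The concern.** With one follow-up there are two patterns: month 6 observed, or month 6 missing. Participants in the second pattern have no month-6 data, so their month-6 mean must come from an assumption. Pattern mixture is a way of making that assumption explicit, but neither document states one. What the SAP does spell out is a repeated-measures model, wording that suits a trial with several visits. On baseline plus month 6 that model predicts the missing values from the observed relation between the two, which is MAR.

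The plan could thus be followed to the letter and report an MNAR sensitivity analysis that never departs from MAR. The trigger adds to this. Observed data cannot show that values are missing not at random. Missingness associated with allocation can be observed, but its absence does not rule MNAR out.

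At stake is how far the results on self-reported outcomes can be relied on. These include the two funder core outcomes, self-reported delinquency (SRDS) and the Strengths and Difficulties Questionnaire (SDQ).

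**Working it through.** **Inputs.**

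- Effect size 0.3, two-sided alpha 0.05, power 80%, 350 evaluable, 370 randomised, 185 per arm (sample size sections of both documents).
- Primary outcome: close to 100% expected, 5% loss allowed (protocol, Sample size calculations); 100% available in the pilot (SAP, Introduction).
- Month-6 assessment: 88% followed up in the pilot, so 12% missing (SAP, Introduction). The target is 70%, so 30% missing if it is only just met (protocol, Risks, item 4).
- Assumed, not in the documents: a shift of 0.5 SD; a baseline-to-month-6 correlation of 0.5 in the simulation.

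**The plan's own figures.** n per arm = 2(1.96 + 0.842)²/0.3² = 174.4, rounded up to 175, or 350 in total. Then 350/0.95 = 368.4, rounded up to 369 and to 370 for equal arms. Both reproduce, so 0.3 SD and 185 per arm serve as the scale below.

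**1. Does the described model depart from MAR?** Simulation with 185 per arm, one baseline, one follow-up and a true effect of zero. Missingness was completely at random in control. In the intervention arm it depended on the month-6 value itself. Over 60 replicates:

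| Quantity | Result |
|---|---|
| Missing, intervention / control | 10.9% / 11.9% |
| Missing minus observed mean, intervention arm | 1.06 SD |
| Estimate with full data | 0.004 SD |
| Complete-case ANCOVA | -0.085 SD |
| Baseline-plus-month-6 mixed model | -0.085 SD |
| Mean absolute difference, ANCOVA v mixed model | 0.002 SD |

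The Monte Carlo error of the ANCOVA mean is about √(2 × 0.75/163)/√60 = 0.096/7.75 = 0.012, so the bias is clear. The mixed model reproduces it. The missing rates in the two arms are nearly equal, so the rates alone would not have met the allocation trigger.

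**2. What would a stated shift do?** Let m be the fraction missing in an arm and δ the amount by which its missing participants differ from the MAR prediction. The arm mean moves by m × δ, and the contrast by m_I × δ_I − m_C × δ_C. With δ = 0.5 SD in one arm only:

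- 12% missing: 0.12 × 0.5 = 0.06 SD
- 30% missing: 0.30 × 0.5 = 0.15 SD, half of 0.3

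Equal m and equal δ in both arms give zero.

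**3. How large a shift would overturn a result?** Take an observed effect of 0.30 SD, equal missingness, a shift in one arm and an unadjusted normal approximation. The critical difference is 1.96 × √(2/[185(1 − m)]), and the tipping δ = (0.30 − critical difference)/m.

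| m | Critical difference (SD) | Tipping δ (SD) |
|---|---|---|
| 5% | 0.209 | 1.82 |
| 12% | 0.217 | 0.69 |
| 30% | 0.244 | 0.19 |

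**4. TLFB.** The outcome has one occasion of measurement, so there is no repeated measure for the mixed model to use. The single baseline frequency item is a different measure. It can serve as a predictor in an imputation model.

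**The case against.** A reader might infer that the planned analysis assumes MAR throughout and cannot test the conclusions. The SAP does not support that. The sentence before the mixed-model sentence names pattern mixture with multiple imputation under varying assumptions, and the protocol names MNAR. Pattern mixture is an MNAR framework and works with one follow-up once the unidentified parameter is set. The MAR criticism applies to the mixed model alone.

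Three other readings also go too far:

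- That the sensitivity model is defined by dropout-time groups. The wording "participants will be grouped based on their dropout time" belongs to the descriptive exploration of the mechanism.
- That suspicion of MNAR is the only trigger. Missingness associated with allocation is a second one, and it can be observed.
- That 30% missing is expected. It is what remains if the 70% target is only just met. The protocol says earlier studies met and exceeded that target, and the pilot reached 88%.

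It is also fair that the Missing data section is framed mainly around the primary outcome. That outcome has a matching six-month baseline count, so a two-occasion model can be fitted to it, and almost no missing data are expected. A one-arm shift is an unfavourable case, since like shifts cancel.

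What stands is that no shift, restriction, reference rule or range appears in either document, the one described model does not suit the design, and the SAP makes conditional what the protocol does not.

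**Conclusion.** The concern holds as a fault in how the MNAR analysis is specified. It is more than missing detail, because the described model and the triggers can be followed exactly without any departure from MAR being examined.

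For the primary outcome the effect is small: near-complete police records are expected, and even at 5% missing it would take a shift of about 1.8 SD in one arm to overturn an observed 0.30 SD. For self-reported secondary outcomes it matters. The contrast moves by 0.06 SD at pilot follow-up and by 0.15 SD at the 70% floor. The tipping shift falls from about 0.69 SD to 0.19 SD. These figures rest on the assumed 0.5 SD shift (for the movement in the contrast), a shift in one arm only, equal missingness by arm and an unadjusted normal approximation (for the tipping points). They show scale and are not forecasts.

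**What to change.** In the SAP's Missing data section:

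- Replace the repeated-measures sentence with delta-adjusted multiple imputation of the month-6 value. Impute under MAR, then shift the imputed values by a stated grid, for example 0 to 0.5 SD worse, in each arm alone and in both. Define the SD used, and say how bounded outcomes such as percent days abstinent are kept in range.
- Report the tipping point for each outcome. Reference-based imputation would be an acceptable alternative if its rule is written down in advance.
- Run it for every outcome with more than 5% missing, primary or secondary, with no trigger, in line with the protocol's Analysis section.
- For TLFB, use the single baseline frequency item in the imputation model. Reconcile the two design tables that list TLFB28 at baseline with the schedules that place it at month 6 only.
- Reword the dropout-time exploration as a comparison of those with and without month-6 data.

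The cost is SAP wording and a short extra analysis. No new data are needed.

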Based on the stage 1 model, we then calculate predicted values of treatment received (\hat{T}) for use in stage 2. The second stage model predicts the substantive outcome (Y e.g. number of offences) using the predicted values of treatment received (\hat{T}) based on the stage 1 model (Eq. 4):

EQ. 5

$$Y = \alpha + \hat{T} + \varepsilon$$

Levels of confidence and p-values

Unless otherwise specified, estimates will be presented with 95% confidence intervals. Significance tests will be two-tailed, and a significance level of <0.05 will be considered statistically significant. For continuous variables a mean difference between the groups and associated 95% confidence interval will be derived, for proportional outcomes the mean difference will be derived using a marginal effects approach, for dichotomous outcomes a relative risk and associated 95% confidence interval compared to a reference value will be presented. This study has a predefined primary outcome measure, at a specific time point and involves a single comparison between two treatment arms, therefore no adjustment for multiplicity is required. As participant randomisation is conducted within site no adjustment for site cluster effects, over and above inclusion of site as a fixed effect covariate, is required.

Presentation of outcomes

As the sample is large, effect size differences will be calculated using Cohen's d, specified in the following equation (Eq. 6):

EQ. 6

$$\delta = (Y_i - Y_c)/S$$

Where Y_i and Y_c are the regression adjusted means, derived from Eq. 1, for the intervention and control groups respectively and S is the pooled standard deviation.

Effect sizes will be reported with 95% confidence intervals and p-values to reflect statistical uncertainty.

References

- FURUKAWA, T. A. & LEUCHT, S. 2011. How to obtain NNT from Cohen's d: comparison of two methods. . *PloS one*, 6.
